### 7.2.1.1 Diary types

Symptom data for this study will be collected using either electronic or paper diaries.

#### 7.2.1.1.1 Electronic Diary

Electronic diaries may be provided by the sponsor for US study centers; the electronic diary collects details associated with symptoms for each episode. The system contains reminders and allows subjects to collect real-time voiding behavior onto a secure server.

### **7.2.1.1.2 Paper Diary**

A paper diary is also available for use in the study. If a paper diary is used, the data will be entered to the RDC database.

### **7.2.1.1.3 Urinary Voiding Diaries**

Symptoms related to OAB and NOUR will be evaluated using either paper or electronic urinary voiding diaries. Subjects will be trained to complete the urinary voiding diaries for 3-days for OAB with diary details collected (such as time, type of episode, urgency, sleep/awake status, etc.) and for 7-days for NOUR with diary details collected (such as time, type of episode, volume, etc.) as part of the Baseline procedures. The urinary voiding diaries will be completed for 3-days for OAB and 7-days for NOUR towards the end of the therapy evaluation and prior to each subsequent follow-up visit. Every effort should be made to remind subjects of the importance of real-time diary completion.

### **7.2.1.1.4 Bowel Diaries**

Symptoms related to FI will be evaluated using either paper or electronic voiding diaries. Subjects will be trained to complete the bowel voiding diary for 7-days as part of the Baseline procedures with diary details collected (such as time, type of episode, urgency, sleep/awake status, etc.). The bowel diaries will be completed for 7-days towards the end of the therapy evaluation [REDACTED]

[REDACTED] Every effort should be made to remind subjects of the importance of real-time diary completion.

## **7.2.1.2 Diary Collection Timepoints**

### **7.2.1.2.1 Baseline Diary**

For subjects who qualify with the overactive bladder indication: The urinary voiding diary will be explained and given to the subject to be completed for 3 consecutive days.

For subjects who qualify with the fecal incontinence indication: The bowel diary will be explained and given to the subject to be completed for 7 consecutive days.

For subjects who qualify with the non-obstructive urinary retention indication: The urinary voiding diary will be explained and given to the subject to be completed for 7 consecutive days.

### **7.2.1.2.2 Therapy Evaluation Period Diary**

The applicable diary for the study cohort diary will be completed towards the end of the therapy evaluation period (completed for 3 consecutive days for OAB, completed for 7 consecutive days for FI and completed for 7 consecutive days for NOUR).

### 7.2.1.2.3 Follow-up visits Diary

Diaries will be collected for each cohort at each follow-up visits (Three-month, Six-month, One-year, and Two-year Follow-up Visits ) and possible unscheduled visit as follow:

- [REDACTED]
- [REDACTED]
- [REDACTED]
- For subjects within the NOUR cohort: The voiding diary will be given to the subject to be completed for 7 days approximately 1 week prior to each follow-up visit.

## 7.3 Center Pooling

There is no a priori provision to exclude any sites from the analysis. The data from all sites will be pooled for analysis. To reduce the possibility of atypical results from a site overly influencing the combined results, no more than 20% subjects, i.e., 12 subjects for OAB cohort, 12 subjects for FI cohort, and 8 subjects for NOUR cohort, will be enrolled at each site unless the site gets pre-approval from the Medtronic for additional enrollments.

## 7.4 Handling of Missing, Unused, and Spurious Data and Dropouts

Missing data are a potential source of bias when analyzing study data. A rigorous study design and execution will help prevent the incidence of missing data from occurring. The potential bias due to missing data depends on the mechanism causing the data to be missing, and the analytical methods applied to amend the missingness.

Subjects who will not pass screening tests will not be used in the analysis as they will not be implanted. After implant, subjects who will be lost to follow-up or will withdraw or discontinued from the clinical investigation without providing data at three-months analysis will be considered missing.

For the primary objective of each cohort, data summaries will be based on those subjects with complete data (CC set), with complete defined as having data at the visit(s) used in analysis (Baseline and 3 months follow up).

All attempts will be made to minimize missing data for primary objective. If 5% of the data or fewer are missing for the analysis, no imputation will be used and the data will be analyzed as specified in the previous section. Otherwise, a sensitivity analysis with multiple imputation will be used for the analysis of the key primary objective.

Prior to the MI, the distribution of the continuous variables will be assessed for normality (using the Shapiro-Wilk test) to determine whether regression ( $P \geq 0.05$ ) or predictive mean matching ( $P < 0.05$ ) multiple imputation will be used for each variable.

- If normality assumption is met, the missing data will be imputed using the fully conditional specification (FCS) method (also known as imputation by chained equations/ICE or sequential generalized regression) in SAS (version 9.4 or higher) with SEED=13951639 and number of imputations=30. After MI procedure, m (m=30) imputed data are obtained. Following imputation of the missing data, change in OAB-q HRQL (OAB cohort) OR CCIS (FI cohort) OR number of CISC (NOUR cohort) will be calculated for each subject within each imputed dataset. The mean and standard error of the change in OAB-q HRQL (OAB cohort) OR CCIS (FI cohort) OR number of CISC (NOUR cohort) will be calculated within each imputed dataset and they will be analyzed using MI analysis methods, with the following specifications:
  - Adjusted degrees of freedom (EDF) = Treated Analysis Set sample size – 1
  - Theta0 = 0
  - Alpha = 0.05
  - ModelEffects = mean change in OAB-q HRQL (OAB cohort) OR CCIS (FI cohort) OR number of CISC (NOUR cohort)
  - StdErr = standard error of change in OAB-q HRQL (OAB cohort) OR CCIS (FI cohort) OR number of CISC (NOUR cohort)

The output ParameterEstimates dataset from the MI analysis will contain the adjusted estimate of the mean and standard error of change in OAB-q HRQL (OAB cohort) OR CCIS (FI cohort) OR number of CISC (NOUR cohort), the 95% confidence interval for the mean change, and the associated t-statistic and p-value from the test of the null hypothesis.

- If normality assumption is not met, the fully conditional method (FCS) with Predictive mean matching (PMM) is chosen to perform multiple imputation for continuous variables (primary objective effectiveness). The Predictive mean matching (PMM) model is implicit (Little and Rubin 2002), which means that there is no need to define an explicit model for the distribution of the missing values. Because of this, predictive mean matching is less vulnerable to model misspecification than the regression methods. The fully conditional method (FCS) does not assume a joint distribution but instead uses a separate conditional distribution for each imputed variable, and FCS method does not require a monotone missing data pattern. The combination of FCS with PMM method is selected due to these reasons. SAS MI procedure will be used with SEED=13951639 and number of imputations=30. After MI procedure, m (m=30) imputed data are obtained. The resulting distribution is likely to be skewed, therefore median will be used to summarize the m imputed datasets instead of mean. The standard error of median calculated from each imputed dataset will be estimated through bootstrap method. Then MIANALYZE procedure is used to combine the results.

The model variables in the MI analysis in both cases (normality and non normality) may include:

- For OAB cohort:
  - Age

- Gender
- Baseline OABq HRQL
- Baseline UUI episodes
- Baseline voids
- Secondary OAB diagnosis: Stress incontinence, Urinary frequency, retention, pelvic pain, interstitial cystitis, or none
- Medical history
- The number of ongoing OAB medications used at baseline
- Motor response at tined lead implant
- For FI cohort:
  - Age
  - Gender
  - Baseline CCIS
  - Baseline movements
  - Baseline accidents
  - Medical history
  - Motor response at tined lead implant
  -
- For NOUR cohort:
  - Age
  - Gender
  - Baseline number of catheterizations
  - Baseline voids
  - Medical history
  - Motor response at tined lead implant

For diary data analyses, although subjects are required to record at least 3 full days (OAB) and at least 7 full days (NOUR/FI) of diary data, missing data imputations will not be performed and all subjects who have at least one full 24-hour period in a visit will be included in analysis for that visit.

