#### 7.9.1.2 Hypothesis

The null ( $H_0$ ) and alternative ( $H_1$ ) hypotheses are:

$$H_0: \mu = 0$$

$$H_a: \mu \neq 0$$

Where  $\mu$  indicates the mean change in OAB-q HRQL total score from Baseline to 3 months post-implant. P-value will be evaluated at alpha level of 0.05.

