#### 7.9.1.4 Analysis Methods and Presentation Format

In case the normality assumption of data will hold (Shapiro Will test), a two-sided one sample t-test will be performed to test the hypothesis described in section 7.9.1.2.

In case the normality assumption of data will not hold (Shapiro Will test), a Wilcoxon Singed Rank test will be performed to test the hypothesis described in section 7.9.1.2.

In addition to the hypothesis testing, the two-sided 95% confidence interval for the mean change in HRQL total score will be calculated and reported.

In cases where subject's OAB-q HRQL total score is missing at Baseline and/or at 3 months post-implant for any reasons, the percentage of missing data will be summarized and a sensitivity analysis using multiple imputation will be performed as described in section 7.4.

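### SAP 7.4: when normality fails, the multiple-imputation sensitivity analysis pools a median, while H0, the reported confidence interval and the normal branch all concern the mean change

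*SAP*

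**What the plan says.** - **Hypothesis.** In SAP 7.9.1.2 the parameter μ "indicates the mean change in OAB-q HRQL total score from Baseline to 3 months post-implant". Sections 7.9.2.2 and 7.9.3.2 define it the same way for CCIS and for CISC per day.
- **Primary analysis.** On complete cases, a one-sample t-test is used if Shapiro-Wilk does not reject normality and a Wilcoxon signed-rank test if it does. Whichever test is used, "the two-sided 95% confidence interval for the mean change in HRQL total score will be calculated and reported" (SAP 7.9.1.4; 7.9.2.4 and 7.9.3.4 say the same for their outcomes).
- **When imputation runs.** "If 5% of the data or fewer are missing for the analysis, no imputation will be used" (SAP 7.4). Above that threshold, Shapiro-Wilk is applied variable by variable to choose regression or predictive mean matching (PMM).
- **Normal branch.** The mean change and its standard error are pooled, giving "the 95% confidence interval for the mean change, and the associated t-statistic and p-value from the test of the null hypothesis". Theta0, Alpha and EDF are listed here.
- **Non-normal branch.** After PMM, "The resulting distribution is likely to be skewed, therefore median will be used to summarize the m imputed datasets instead of mean". The median's standard error is bootstrapped. "Then MIANALYZE procedure is used to combine the results". Theta0, Alpha and EDF are not repeated, and no imputed mean is specified.
- **Descriptives.** SAP 7.2 lists medians alongside means for continuous measures.
- **Purpose.** CIP 13.1.1 says the sensitivity analyses are there to assess how missing data affect the primary objective.

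**The concern.** A sensitivity analysis for missing data is informative when only the missing-data handling changes. In this branch the summary measure changes too. The imputed result can then sit away from the primary mean and interval even if the missing subjects resemble the observed ones. PMM does not require the switch: it deals with non-normality when values are imputed, and the mean can be pooled afterwards.

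Under non-normality the plan would report three results on different footings: a Wilcoxon p-value (under skewness, in general a test of neither mean nor median), an interval for the mean, and an imputed median. Because the branch is chosen per variable, a t-test on the mean could also be paired with a median-based imputation. At stake is how the sensitivity analysis is read, not the primary result.

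**Working it through.** **1. The plan's own figure.** The study was sized on the mean. With noncentrality (mean/SD)·√n at two-sided 0.05 (SAP section 6):
- OAB: 30/27·√50 = 7.86, power above 0.9999.
- FI: 5/6.2·√50 = 5.70, power 0.9999 (also with SD 6).
- NOUR: 2/3·√30 = 3.65, power 0.942.

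The stated power above 90% is reproduced and is not in dispute.

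**2. Gap between mean and median with nothing missing.** Assumed shape: gamma, since the documents give none. In SD units the gap is 0.164 at skewness 1 (shape 4) and 1 − ln 2 = 0.307 at skewness 2 (shape 1). Multiplied by the SD:
- OAB (27): 4.4 to 8.3 points.
- FI (6.2): 1.0 to 1.9 points.
- NOUR (3): 0.5 to 0.9 CISC/day.

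The median shows less improvement than the mean if the long tail runs to larger improvement, and more if it runs the other way.

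**3. A scale for that gap.** CIP 13.1.1 expects attrition below 10% by 3 months. If 10% were missing and none of them had changed at all, the mean would fall by 10% of the planned change: 3.0, 0.5 and 0.2. The gap in step 2 is 1.5–2.8, 2.0–3.8 and 2.5–4.6 times as large.

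**4. Separating the two effects.** Simulation: N = 60, 60 and 40; 10% missing completely at random; PMM with 5 donors and one covariate; m = 30; tail to larger improvement; 200 trials per cell. Improvement is shown as positive.

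| Cohort, skewness | Complete-case mean | Imputed mean | Imputed median | Shift from imputation | Shift from summary measure |
|---|---|---|---|---|---|
| OAB, 1 | 29.98 | 29.98 | 25.74 | −0.005 | −4.24 |
| OAB, 2 | 30.18 | 30.10 | 22.27 | −0.077 | −7.83 |
| FI, 1 | 5.06 | 5.06 | 4.07 | −0.005 | −0.99 |
| FI, 2 | 5.03 | 5.01 | 3.18 | −0.022 | −1.83 |
| NOUR, 1 | 2.04 | 2.04 | 1.59 | −0.004 | −0.45 |
| NOUR, 2 | 2.08 | 2.07 | 1.20 | −0.009 | −0.87 |

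Nearly all of the movement comes from the summary measure.

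**5. Against the primary interval.** Among simulated trials in which Shapiro-Wilk rejects normality of the change, the imputed median lies outside the complete-case 95% interval for the mean (t-based here) in 13–18% (skewness 1) and 63–72% (skewness 2) of OAB and FI trials, and in 6–8% and 32–38% of NOUR trials. The imputed mean does so in 0%.

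**6. Can the branch be reached?** Reading the threshold as 5% of implanted subjects, imputation needs at least 4 of 60 or 3 of 40 missing. At true attrition of 5–9% the binomial probability is 35–80% (N = 60) and 32–71% (N = 40).

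**7. Significance.** This assumes that the pooled median is tested against 0 with EDF = N − 1, which the SAP does not state for this branch. NOUR trials with a significant primary Wilcoxon but a non-significant imputed median, out of all trials at 5/7/9% attrition: 6/10/14% (skewness 1) and 13/25/31% (skewness 2) with the tail to larger improvement; imputed mean 0%. With the opposite tail: median 0.1–0.8%, mean 0.7–3.6%. In FI the median loses at most about 3% under skewness (3–8% for a uniform shape); in OAB under 1%.

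**8. Symmetric change.** With baseline and 3-month scores both gamma (shape 4, correlation 0.5), 73–91% of trials had a non-normal score. Only 22–29% of those had a non-normal change, and the mean–median gap averaged 0.00 SD.

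**The case against.** The strongest reply is that the plan does supply a comparator. SAP 7.2 reports medians with means, and SAP 7.9 asks for descriptive statistics of the change, so the complete-case median will stand beside the imputed one. Under missingness completely at random the two agree almost exactly in simulated trials that enter the branch: OAB 24.95 and 24.96 (skewness 1), 21.89 and 21.89 (skewness 2); NOUR 1.31 and 1.31, 1.10 and 1.10. This stands. A reader might infer that a missing-data effect could not be told apart from the switch at all; for the point estimate it can be, roughly. What is missing is an interval or test for the complete-case median, and any imputed result on the scale of H0 and the reported interval.

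A second reply is that a median is a natural companion to the Wilcoxon test, and that pooling the mean pairs a t-type p-value with a Wilcoxon p-value. That is a real cost. Even so, the plan's stated parameter and interval are on the mean.

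Third, the sizes depend on assumed skewness of the change, whereas the SAP checks each variable. Step 8 shows that skewed scores can give a symmetric change and no gap. In NOUR, improvement cannot exceed the baseline count, so the unbounded tail in step 7 is unfavourable to the median. Both limits stand.

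Finally, a reader might infer that SAP 7.4 contradicts itself by imputing CISC while saying of diary data that "missing data imputations will not be performed and all subjects who have at least one full 24-hour period in a visit will be included". That sentence concerns full diary days and reads naturally as covering missing days within a diary. It is at most an ambiguity, and the OAB and FI outcomes are questionnaires in any case.

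**Conclusion.** The mismatch is in the text and holds for all three cohorts. Its size is conditional: about 0.16 to 0.31 SD if the change has skewness 1 to 2 (gamma shapes, missing completely at random), and about 0 if the change is symmetric. The branch also requires more than 5% missing and a failed normality check.

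A reader might infer that the primary finding is at risk. The documents do not support that: the primary analysis is on complete cases, and the SAP attaches no decision rule to the imputed result. Any effect on a significance verdict is essentially confined to NOUR, under assumed shapes and an EDF that the SAP does not state for this branch. Severity: minor.

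**What to change.** In SAP 7.4:
- Keep fully conditional specification with PMM for non-normal variables.
- In both branches, compute the mean change and its standard error in each imputed dataset and pool them with MIANALYZE, using Theta0 = 0, Alpha = 0.05 and EDF = FAS size − 1. The current text reads "Adjusted degrees of freedom (EDF) = Treated Analysis Set sample size" minus 1, but SAP 7.1.3 defines no such set, and 7.9.1.5, 7.9.2.5 and 7.9.3.5 give FAS for this analysis.
- State that this result is compared with the complete-case mean change and its interval.
- Keep the pooled median as a supplementary result. Say explicitly that it is the median change, and set it beside the complete-case median change with the same bootstrap interval.

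The primary t-test/Wilcoxon rule stays as it is. Only SAP text changes, because CIP 13.1.3 leaves the imputation details to the SAP. The downsides are small. In this branch the imputed p-value for the mean sits beside a primary Wilcoxon p-value. If the tail runs to less improvement, the NOUR imputed mean loses significance slightly more often than the imputed median (0.7–3.6% against 0.1–0.8% of all simulated trials).

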**Therapy Evaluation**

The therapy evaluation period should be conducted in accordance with the labeling using the Verify® external neurostimulator and should not exceed the therapy evaluation duration for the specific geography.

A study diary will be completed towards the end of the therapy evaluation period (completed for 3 consecutive days for overactive bladder, completed for 7 consecutive days for fecal incontinence and for non-obstructive urinary retention). Therapeutic success must be achieved in order to qualify for a neurostimulator implant in the study.

Any [REDACTED] reportable adverse events/device deficiencies will be documented and reported. [REDACTED]

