## Therapy Evaluation

The therapy evaluation period should be conducted in accordance with the labeling using the Verify external neurostimulator and should not exceed the therapy evaluation duration for the specific geography.

The applicable diary for the study cohort diary will be completed towards the end of the therapy evaluation period (completed for 3 consecutive days for OAB, completed for 7 consecutive days for FI and completed for 7 consecutive days for NOUR). Therapeutic success must be achieved in order to qualify for a neurostimulator implant in the study. A successful therapy evaluation is recommended as:

- 50% or greater improvement from baseline in average voids/day or a return to normal voiding (less than 8 voids/day) for subjects with urgency frequency at baseline\*
- 50% improvement from baseline in average leaks/day for subjects with urinary incontinence at baseline\*
- 50% improvement from baseline in average fecal incontinence episodes/week for subjects with fecal incontinence at baseline
- 50% reduction from baseline in average number of CISC/day for subjects with non-obstructive urinary retention at baseline

\*Subjects with both urgency frequency and urinary urge incontinence at baseline must meet at least one of the above criteria to be considered a success.

Any [REDACTED] reportable adverse events/device deficiencies will be documented and reported. [REDACTED]

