### **Medtronic Controlled Information**

## Urinary Voiding Diary

Symptoms related to OAB and NOUR will be evaluated using either paper or electronic voiding diaries. Subjects will be trained to complete the urinary voiding diaries for 3-days for OAB with diary details collected (such as time, type of episode, urgency, sleep/awake status, etc.) and for 7-days for NOUR with diary details collected (such as time, type of episode, volume, etc.) as part of the baseline procedures. The urinary voiding diaries will be completed for 3-days for OAB and 7-days for NOUR towards the end of the therapy evaluation and prior to each subsequent follow-up visit. Every effort should be made to remind subjects of the importance of real-time diary completion.

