### 7.9.1.5 Determination of Subject for Analysis

The primary analysis will include all complete case subjects (CC) who have data available at Baseline and Three-months follow up visit. Sensitivity analysis will include all implanted subjects (FAS) by imputing missing data as described in section 7.4.

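### The candidate predictors for multiple imputation omit the therapy-evaluation diary response, so the sensitivity analysis may stay close to the complete-case result if weak test responders are lost before month 3

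*SAP*

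**What the plan says.** In each cohort the primary analysis uses complete cases at baseline and month 3. Multiple imputation is the sensitivity analysis: "Sensitivity analysis will include all implanted subjects (FAS) by imputing missing data as described in section 7.4" (SAP 7.9.1.5; the FI and NOUR sections say the same, the FI one with a different section number). It is conditional: "If 5% of the data or fewer are missing for the analysis, no imputation will be used" (SAP 7.4).

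The predictors are introduced permissively: "The model variables in the MI analysis in both cases (normality and non normality) may include". The readable entries are:

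- **All cohorts:** age, gender, baseline values, medical history and "Motor response at tined lead implant".
- **OAB only, in addition:** secondary diagnosis and number of OAB medications.

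The plan also schedules a measurement under stimulation before implant. SAP 7.2.1.2.2 states: "The applicable diary for the study cohort diary will be completed towards the end of the therapy evaluation period". Protocol 9.5 says the same of the urinary diaries: "The urinary voiding diaries will be completed for 3-days for OAB and 7-days for NOUR towards the end of the therapy evaluation". Passing this phase is the condition for implant: "Therapeutic success must be achieved in order to qualify for a neurostimulator implant in the study" (Protocol 9.1, Therapy Evaluation). For NOUR the recommended success measure is "50% reduction from baseline in average number of CISC/day for subjects with non-obstructive urinary retention at baseline", which is the quantity of the NOUR primary endpoint.

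**The concern.** Multiple imputation corrects for selective loss only as far as its predictors explain both who is lost and what their outcome would have been. Apart from motor response, the readable lists hold nothing recorded after baseline. The most direct early evidence of how a subject responds to stimulation is collected but not named.

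Loss related to response is foreseeable. Protocol 6 exits subjects whose device is permanently explanted, and Protocol 9.9 gives lack of efficacy as an example of a reason for withdrawal. If such subjects also tended to be weak test responders, a model without test response would impute them like stronger responders with the same baseline. The sensitivity analysis would then appear to support the complete-case estimate while hardly testing it. It is the only readable sensitivity analysis of the primary objective for missing data.

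**Working it through.** **1. Planning figures reproduced.** For a two-sided one-sample t-test at alpha 0.05, the noncentrality is sqrt(n) × mean / SD, with inputs from Protocol 13.1.1 and SAP 6.

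| Cohort | n | Mean / SD | Noncentrality | Power |
|---|---|---|---|---|
| OAB | 50 | 30 / 27 | 7.86 | >0.9999 |
| FI | 50 | 5 / 6.2 | 5.70 | 0.9999 |
| NOUR | 30 | 2 / 3 | 3.65 | 0.942 |

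The stated power above 90% holds in each cohort. For FI it also holds with the SD of 6 used elsewhere in the plan (0.9999).

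**2. When imputation runs.** 5% of 60 is 3 and 5% of 40 is 2, so it starts at 4 missing of 60 (OAB, FI) or 3 missing of 40 (NOUR). Protocol 13.1.1 expects less than 10% attrition by month 3.

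**3. NOUR simulation.** From the plan: n = 40, mean change −2 CISC/day, SD 3. Assumed: baseline correlates −0.4 with both test-phase and month-3 change; test-phase and month-3 change correlate at rho; dropout is logistic in test-phase change (more likely with a weaker response), set to 10% missing. Missing values are imputed by regression on baseline alone, or on baseline plus test-phase change. The bias is measured against the full-data mean over 4000 replicates.

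Overstated reduction, CISC/day:

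| Dropout slope (log-odds per SD) | Imputation model | rho 0.3 | rho 0.5 | rho 0.7 |
|---|---|---|---|---|
| 1.5 | complete case | 0.11 | 0.18 | 0.26 |
| 1.5 | baseline only | 0.05 | 0.13 | 0.20 |
| 0.7 | baseline only | 0.03 | 0.07 | 0.11 |

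Adding test-phase change brings the bias to 0.003 or less in absolute value. The range 0.03 to 0.20 is 0.03/2 = 1.5% to 0.20/2 = 10% of the planned change, or 0.01 to 0.07 SD.

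**4. Second simulation, all cohorts.** Regression imputation with m = 30 and Rubin's rules, 600 runs, N = 60/60/40, about 10% missing, slope 1.5. Here one baseline covariate correlates 0.3 with month-3 change and is independent of test response.

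| Cohort (planned change) | Overstatement without test response, rho 0.3 / 0.5 / 0.7 | With test response |
|---|---|---|
| OAB (30) | 0.95 / 1.73 / 2.70 | −0.05 / −0.02 / 0.26 |
| FI (5) | 0.17 / 0.41 / 0.55 | −0.06 / 0.03 / 0.00 |
| NOUR (2) | 0.09 / 0.21 / 0.23 | −0.03 / 0.03 / −0.03 |

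The Monte Carlo error for NOUR is about 3/sqrt(36)/sqrt(600) = 0.02. In this setting imputation without test response matches complete case (OAB, rho 0.5: 1.73 against 1.72). At rho = 0 there is no bias to remove. Rejection rates are 1.000 for OAB and FI and at least 0.949 for NOUR, with or without test response.

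**5. Extreme case.** If the lowest 10% of test responders are all lost and nothing else predicts the outcome, the shift is rho × SD × phi(z)/(1 − q) = rho × SD × 0.195. For NOUR this is 0.18 / 0.29 / 0.41 CISC/day.

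**6. Dropout driven by the month-3 outcome itself.** Adding test response removes only part of the bias (OAB, rho 0.5: 3.17 falls to 2.41).

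**The case against.** **The list is permissive.** A reader might infer that the model is restricted to the listed variables. The SAP does not say so: its wording neither fixes the model nor rules out test response. The FI list also ends in an empty bullet, which may be a stray mark or lost text. What stands is that no readable entry names the diary response.

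**The bias is not established.** A reader might infer that weak responders who leave will be imputed too favourably. The documents give no correlation between test response and month-3 change and no dropout model. The requirement of test success narrows the range of response among implanted subjects. If 70% pass (an assumption) and the correlations describe subjects before that selection, they shrink to 0.22 / 0.38 / 0.57 and the NOUR bias at slope 1.5 to 0.03 / 0.07 / 0.12. A slope of 1.5 is also steep, an odds ratio of about 4.5 per SD. The simulated models stand in for the listed one without motor response or the other listed predictors. Removal of the bias follows by construction, because dropout was generated from test response. These points limit the size and make the claim conditional.

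**A larger figure is tempting.** With 20% missing, rho 0.7 and slope 1.5, the NOUR bias reaches 0.38 CISC/day, 19% of the planned change. Protocol 13.1.1 gives about 20% as the two-year attrition, not the month-3 figure, so this is not the relevant case.

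**Baseline variables may already help.** When baseline correlates with test response, baseline-only imputation removes some of the bias (0.11 to 0.05 at rho 0.3, and about a quarter at 0.5 and 0.7). It does not always mirror complete case.

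**OAB and FI differ from NOUR.** Their endpoints are questionnaires and the diary is another instrument, so the gain there is less certain. The SAP does already list baseline diary counts as predictors in those cohorts.

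**Conclusion.** The point holds in conditional form and is strongest for NOUR. The readable predictor lists leave out a planned on-stimulation measurement that is a natural predictor of the month-3 outcome. If early loss is related to test response, and test response predicts month-3 change beyond the listed variables, the sensitivity analysis keeps much or all of the complete-case bias.

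Under the step 3 assumptions the size is modest: about 0.03 to 0.20 CISC/day of a planned 2, with about 10% missing. The step 4 baseline assumption gives up to 0.23. It affects the estimated change and its interval in a sensitivity analysis that runs only above 5% missing. It does not affect the primary complete-case analysis, and under the planning assumptions it does not change the test against zero. The documents do not support a claim that the primary conclusion is at risk.

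**What to change.** In SAP 7.4, name the therapy-evaluation diary change from baseline as a required imputation predictor instead of leaving it to a permissive list:

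- **NOUR (first priority):** CISC/day.
- **OAB:** voids/day and leaks/day.
- **FI:** incontinence episodes/week.

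Two further steps are optional. The primary outcome at later visits can be added; it helps only subjects who miss month 3 alone, not those who have left. The open-ended medical-history term can be dropped to keep the model small.

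The cost is SAP wording and one or two more predictors in cohorts of 40 to 60. No new data are needed, because the diaries are already scheduled. The change does not address dropout that depends on the unobserved month-3 outcome; a delta-adjusted analysis would be needed for that.
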